### 5.2.2 Timing of Dose Administration

Trial treatment should be administered on Day 1 of each cycle after all procedures/assessments have been completed as detailed on the Trial Flow Chart (Section 6.0). Trial treatment may be administered up to 3 days before or after the scheduled Day 1 of each cycle due to administrative reasons.

All trial treatments will be administered on an outpatient basis.

Pembrolizumab 200 mg will be administered as a 30 minute IV infusion every 3 weeks. The site should make every effort to target infusion timing to be as close to 30 minutes as possible. However, given

the variability of infusion pumps from site to site, a window of -5 minutes and +10 minutes is permitted (i.e., infusion time is 30 minutes: -5 min/+10 min).

The Pharmacy Manual contains specific instructions for the preparation of the pembrolizumab infusion fluid and administration of infusion solution.

### **5.2.3 Trial Blinding/Masking**

This is an open-label trial; therefore, the investigator and subject will know the treatment administered.

## **5.3 Concomitant Medications/Vaccinations (allowed & prohibited)**

Medications or vaccinations specifically prohibited in the exclusion criteria are not allowed during the ongoing trial. If there is a clinical indication for one of these or other medications or vaccinations specifically prohibited during the trial, discontinuation from trial therapy or vaccination may be required. The investigator should discuss any questions regarding this with the Merck Clinical team. The final decision on any supportive therapy or vaccination rests with the investigator and/or the subject's primary physician.

### **5.3.1 Acceptable Concomitant Medications**

All treatments that the investigator considers necessary for a subject's welfare may be administered at the discretion of the investigator in keeping with the community standards of medical care. All concomitant medication will be recorded on the case report form (CRF) including all prescription, over-the-counter (OTC), herbal supplements, and IV medications and fluids. If changes occur during the trial period, documentation of drug dosage, frequency, route, and date may also be included on the CRF.

All concomitant medications received within 28 days before the first dose of trial treatment and 30 days after the last dose of trial treatment should be recorded. Concomitant medications administered after 30 days after the last dose of trial treatment should be recorded for SAEs and ECIs as defined in Section 7.2.

### **5.3.2 Prohibited Concomitant Medications**

Subjects are prohibited from receiving the following therapies during the Screening and Treatment Phase (including retreatment for post-complete response relapse) of this trial:

- Antineoplastic systemic chemotherapy or biological therapy
- Immunotherapy not specified in this protocol
- Chemotherapy not specified in this protocol
- Investigational agents other than pembrolizumab
- Radiation therapy

- Note: Radiation therapy to a symptomatic solitary lesion or to the brain may be allowed at the investigator's discretion.
- Live vaccines within 30 days prior to the first dose of trial treatment and while participating in the trial. Examples of live vaccines include, but are not limited to, the following: measles, mumps, rubella, varicella/zoster, yellow fever, rabies, BCG, and typhoid vaccine.
- Systemic glucocorticoids for any purpose other than to modulate symptoms from an event of clinical interest of suspected immunologic etiology. The use of physiologic doses of corticosteroids may be approved.

Subjects who, in the assessment by the investigator, require the use of any of the aforementioned treatments for clinical management should be removed from the trial. Subjects may receive other medications that the investigator deems to be medically necessary.

The Exclusion Criteria describes other medications which are prohibited in this trial.

There are no prohibited therapies during the Post-Treatment Follow-up Phase.

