## 2.0 TRIAL DESIGN

### 2.1 Trial Design

Specific procedures to be performed during the trial, as well as their prescribed times and associated visit windows, are outlined in the Trial Flow Chart - Section 6.0. Details of each procedure are provided in Section 7.0 – Trial Procedures.

This is a single-site Phase II trial of intravenous (IV) pembrolizumab in subjects with non-small cell lung cancer (NSCLC) with PD-L1 positive ( $\geq 1\%$  by immunohistochemistry (IHC) 22C3 pharmDx test) and EGFR mutant tumors who have not been previously treated with a tyrosine kinase inhibitor (TKI). Approximately 25 subjects will be enrolled in this trial to examine the response to pembrolizumab in this TKI-naïve population. Subjects will all receive 200 mg every 3 weeks (Q3W). Assignment to pembrolizumab will be unblinded.

Subjects will be evaluated every 9 weeks (63 +/- 7 days) with radiographic imaging to assess response to treatment. All imaging obtained on study will be assessed using a modified Response Evaluation Criteria in Solid Tumors (RECIST) 1.1 for determination of objective response rate (ORR) and progression-free survival (PFS). Subjects will continue with the assigned study treatment until RECIST 1.1-defined progression of disease, unacceptable toxicity, intercurrent illness that prevents further administration of treatment, investigator's decision to withdraw the subject, subject withdraws consent, pregnancy of the subject, noncompliance with trial treatment or procedure requirements, administrative reasons, or the subject has received 35 trial treatments of pembrolizumab. Treatment may continue despite RECIST 1.1 defined progression if the subject is clinically stable and is considered to be deriving clinical benefit by the investigator. Adverse events will be monitored throughout the trial and graded in severity according to the guidelines outlined in the NCI Common Terminology Criteria for Adverse Events (CTCAE) version 4.0.

After the end of treatment, each subject will be followed for a minimum of 30 days for adverse event monitoring. After progression on pembrolizumab, patients will be asked to undergo an additional biopsy and blood draw and be followed through periodic follow-up visits and calls (every 60 days) for evaluation of duration of response with the EGFR TKI as well as survival follow up. Subjects will have post-treatment follow-up for disease status until death, withdrawing consent, or becoming lost to follow-up.

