### **5.1.3 Subject Exclusion Criteria**

The subject must be excluded from participating in the trial if the subject:

1. Has received prior therapy with an EGFR tyrosine kinase inhibitor (such as erlotinib, gefitinib, afatinib, rociletinib, or AZD9291) for NSCLC.
2. Is currently participating or has participated in a study of an investigational agent or using an investigational device within 30 days of the first dose of trial treatment. The 30 day window should be applied to the last dose of an antineoplastic investigational agent or last use of an investigational device with antineoplastic intent.
3. Is receiving systemic steroid therapy within three days prior to the first dose of trial treatment or receiving any other form of immunosuppressive medication (corticosteroid use on study for management of ECIs is allowed).
4. Is expected to require any other form of systemic or localized antineoplastic therapy while on trial (including maintenance therapy with another agent for NSCLC or radiation therapy).
5. Has received prior systemic cytotoxic chemotherapy, antineoplastic biological therapy (e.g., cetuximab), major surgery within 3 weeks of the first dose of trial treatment; received thoracic radiation therapy of > 30 Gy within 6 months of the first dose of trial treatment.
6. Has received prior therapy with an anti-PD-1, anti-PD-L1, anti-PD-L2, anti-CD137, or anti-Cytotoxic T-lymphocyte-associated antigen-4 (CTLA-4) antibody (including ipilimumab or any other antibody or drug specifically targeting T-cell co-stimulation or checkpoint pathways). Has participated in another pembrolizumab clinical trial.

7. Has a known history of prior malignancy that in the opinion of the investigator interferes with the ability to interpret the radiographic results (e.g. a second active malignancy with some lesions being of uncertain origin).
8. Subjects with central nervous system (CNS) metastases and/or carcinomatous meningitis may participate provided they are clinically stable, and are using no steroids for at least seven days prior to study medication.

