## 5.6 Subject Withdrawal/Discontinuation Criteria

Subjects may withdraw consent at any time for any reason or be dropped from the trial at the discretion of the investigator should any untoward effect occur. In addition, a subject may be withdrawn by the investigator or the UCLA DSMB if enrollment into the trial is inappropriate, the trial plan is violated, or for administrative and/or other safety reasons. Specific details regarding discontinuation or withdrawal are provided in Section 7.1.4 – Other Procedures.

A subject must be discontinued from the trial for any of the following reasons:

- The subject or legal representative (such as a parent or legal guardian) withdraws consent.
- Confirmed radiographic disease progression

*Note:* For unconfirmed radiographic disease progression, please see Section 5.2.2

*Note:* A subject may continue on treatment with confirmed radiographic progression if clinically stable or clinically improved. Unacceptable adverse experiences as described in Section 5.2.1.2

- Unacceptable adverse experiences as described in Section 5.2.1.2
- Intercurrent illness that prevents further administration of treatment

- Investigator's decision to withdraw the subject
- The subject has a confirmed positive serum pregnancy test
- Noncompliance with trial treatment or procedure requirements
- The subject is lost to follow-up
- Completed 24 months of uninterrupted treatment with pembrolizumab or 35 administrations of study medication, whichever is later.

*Note: 24 months of study medication is calculated from the date of first dose. Subjects who stop pembrolizumab after 24 months may be eligible for up to one year of additional study treatment if they progress after stopping study treatment provided they meet the requirements detailed in Section 7.1.5.5*

- Administrative reasons

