The End of Treatment and Follow-up visit procedures are listed in Section 6 (Protocol Flow Chart) and Section 7.1.5 (Visit Requirements). After the end of treatment, each subject will be followed for 30 days for adverse event monitoring (serious adverse events will be collected for 90 days after the end of treatment as described in Section 7.2.3.1). Subjects who discontinue for reasons other than progressive disease will have post-treatment follow-up for disease status until disease progression, initiating a non-study cancer treatment, withdrawing consent or becoming lost to follow-up. After documented disease progression each subject will be followed by telephone for overall survival until death, withdrawal of consent, or the end of the study, whichever occurs first.

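### Sections 5.3 and 5.3.2 disagree on whether needing a prohibited treatment ends study therapy or trial participation; read literally, 5.3.2 could cut follow-up short and censor PFS informatively

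*Combined protocol and SAP*

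**What the plan says.** Section 5.3.2 lists therapies prohibited during screening and treatment: other anticancer and investigational agents, radiation, live vaccines, and systemic glucocorticoids outside stated exceptions. It then directs that subjects who, in the investigator's view, "require the use of any of the aforementioned treatments for clinical management should be removed from the trial". Its parent section, 5.3, covers clinical need for a prohibited medication or vaccine and says that "discontinuation from trial therapy or vaccination may be required".

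On follow-up, section 2.1 says: "Subjects will have post-treatment follow-up for disease status until death, withdrawing consent, or becoming lost to follow-up". Section 5.6 gives a different set of end points for subjects who stop for reasons other than progressive disease. They have "post-treatment follow-up for disease status until disease progression, initiating a non-study cancer treatment, withdrawing consent or becoming lost to follow-up".

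Two further sentences in 5.3.2 bear on the reading. One limits the radiation ban: "Radiation therapy to a symptomatic solitary lesion or to the brain may be allowed at the investigator's discretion". The other closes the section: "There are no prohibited therapies during the Post-Treatment Follow-up Phase".

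**The concern.** Stopping a drug and leaving a trial have different consequences for time-to-event endpoints. A patient who stops pembrolizumab and stays under observation still contributes a progression date and a death date. A patient who leaves the trial is censored on that day.

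Several triggers in 5.3.2 can plausibly accompany deterioration: a new systemic anticancer drug, radiation beyond the permitted exception, or systemic steroids for a symptom that is not immune-related. The last is realistic here, because exclusion criterion 8 in 5.1.3 admits clinically stable patients with CNS metastases who "are using no steroids for at least seven days prior to study medication". If such patients left follow-up before progression was documented, the censoring would be related to prognosis and Kaplan-Meier PFS would tend to be too favourable. The secondary objective on TKI therapy after pembrolizumab (3.2) also needs these patients to remain observed. With about 25 patients and no replacement (5.7), a few departures could matter.

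**Working it through.** **1. The plan's own figure.** Section 9.6 states 81% power for ORR with 25 patients, 10% against 26%, exact binomial test, one-sided 0.10. The smallest number of responders r with P(X ≥ r | 25, 0.10) ≤ 0.10 is 5: r = 4 gives 0.2364 and r = 5 gives 0.0980. Power is P(X ≥ 5 | 25, 0.26) = 0.817, which agrees. Section 9.1 puts every patient with measurable baseline disease and at least one dose in the Full Analysis Set, so removal under 5.3.2 does not change the ORR denominator. No power or event target is stated for PFS or OS.

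**2. Does another section keep the patient in follow-up?** Two kinds of patient are traced: A starts a new anticancer drug; B needs a systemic steroid and has no documented progression.

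| Section | Who enters | When it ends | A | B |
|---|---|---|---|---|
| 2.1, disease status | Subjects after treatment | Death, withdrawn consent, loss to follow-up | Continues | Continues |
| 5.6, disease status | Stopped for a reason other than progression | Progression, non-study cancer treatment, withdrawn consent, loss to follow-up | Ends | Continues, if removal counts as stopping |
| 5.6, survival calls | After documented progression | Death, withdrawn consent, end of study | Only once progression is documented | Not triggered |
| 7.1.1.5.3 | New anticancer therapy started | Moves to survival follow-up | Covered | Not triggered |
| 7.1.5.4, imaging every 63 ± 7 days | Discontinued trial treatment without progression | No end stated | Covered, if removal means stopping treatment | Same condition |
| 7.1.5.4.1, visits with scans about every 2 months | After the follow-up visits | Death, withdrawn consent, end of study | Covered | Covered, by way of 7.1.5.4 |

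**3. What follows for each endpoint.**

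- OS: patient A is held by 7.1.1.5.3 whatever 5.3.2 means. Patient B is held by 7.1.5.4 and 7.1.5.4.1, provided that removal is read as stopping treatment.
- PFS, patient B: protected under the same condition. On the literal reading, follow-up ends before progression.
- PFS, patient A: exposed even on the generous reading. Section 5.6 stops disease-status follow-up at the new treatment, 2.1 does not, and 7.1.5.4.1 continues scans. Section 9.1 has no censoring rule to settle which governs.

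**4. Size.** The documents give no number of removals, so no bias can be computed from them. An illustration on assumed inputs shows direction only. It takes 25 exponential event times with complete follow-up and censors k patients at 30% to 100% of their own event time.

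| Assumed k removed | Median overstated, k drawn from the 2k shortest times | Median overstated, k drawn at random |
|---|---|---|
| 1 | about 4% | about 5% |
| 2 | about 13% | about 8% |
| 3 | about 24% | about 11% |
| 5 | about 40% | about 19% |

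Even the random draw is biased, because the censoring time is tied to the event time by construction. These are not estimates for this trial: k, the timing and the link to prognosis are all assumed, and the effect vanishes if follow-up continues.

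**The case against.** The strongest reply is that this protocol uses the word trial loosely. Section 5.6 opens its list with "A subject must be discontinued from the trial for any of the following reasons", and the list includes radiographic progression and completion of treatment. The same section then requires follow-up of those patients. If leaving the trial ended observation, survival after progression and the TKI objective could not be studied at all. Section 5.3.2 itself expects the listed therapies to be used later, since it lifts all prohibitions in post-treatment follow-up. Need for a prohibited therapy can also fall under the investigator's decision to withdraw, which 5.6 lists, and the disease-status sentence in 5.6 covers anyone who stops for a reason other than progression. Serious adverse event reporting in 7.2.3.1 makes no exception for removed subjects.

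Most of this stands. A reader might infer from 5.3.2 that OS loses these patients. The documents do not support that: 7.1.1.5.3, 7.1.5.4 and 7.1.5.4.1 provide for their survival follow-up, and no section says that removal ends it. A reader might also infer that those removed are the sickest patients. That is not established either. The list includes live vaccines, radiation to the brain or to a symptomatic solitary lesion may be allowed, physiologic steroid doses may be approved, and no removal rate is given.

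The reply does not remove the conflict between 5.3 and 5.3.2. For a patient who needs steroids and has no documented progression, neither 7.1.1.5.3 nor the survival calls in 5.6 apply, so retention depends on reading removal from the trial as stopping treatment. Section 5.3.2 does not say that. The mismatch between 5.6 and 2.1 remains on any reading.

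**Conclusion.** The contradiction between 5.3 and 5.3.2 is real and should be reconciled. Its likely statistical consequence is limited: possible informative censoring, mainly in PFS, if a site takes 5.3.2 literally. A separate part of the PFS exposure comes from 5.6 ending disease-status follow-up at a non-study cancer treatment, against 2.1 and 7.1.5.4.1. OS is largely protected if 5.6, 7.1.1.5.3, 7.1.5.4 and 7.1.5.4.1 are applied as written, and the ORR denominator and the 81% power figure are untouched.

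The direction, PFS too favourable, rests on the assumption that removal is related to prognosis. The size cannot be stated, because the number and timing of removals are unknown. The case for acting is that the correction is cheap, while observations lost through a literal reading may not be recoverable.

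**What to change.** Make three edits at the next amendment:

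1. Reconcile 5.3 and 5.3.2 so that they give one instruction for clinical need of a prohibited treatment. Whether pembrolizumab stops is for the clinical team to decide.
2. Add to 5.3.2, in place of the direction to remove the subject from the trial, a sentence such as: *Whatever is decided about pembrolizumab, the subject remains in follow-up for disease status, safety, subsequent TKI therapy and survival unless consent is withdrawn.*
3. Align the disease-status sentence in 5.6 with 2.1 and 7.1.5.4, so that starting a non-study cancer treatment does not end disease-status follow-up in one section and continue it in another.

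Changing 5.3.2 alone would leave the PFS problem in 5.6 in place. These edits also do not supply the PFS censoring rule that 9.1 lacks; that needs its own sentence.

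The cost is a few sentences. The imaging, visits and calls are already planned, so the added work is to continue them for however many patients are affected.

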## 5.4 Rescue Medications & Supportive Care

### 5.4.1 Supportive Care Guidelines

Subjects should receive appropriate supportive care measures as deemed necessary by the treating investigator. Suggested supportive care measures for the management of adverse events with potential immunologic etiology are outlined below. Where appropriate, these guidelines include the use of oral or intravenous treatment with corticosteroids as well as additional anti-inflammatory agents if symptoms do not improve with administration of corticosteroids. Note that several courses of steroid tapering may be necessary as symptoms may worsen when the steroid dose is decreased. For each disorder, attempts should be made to rule out other causes such as metastatic disease or bacterial or viral infection, which might require additional supportive care. The treatment guidelines are intended to be applied when the investigator determines the events to be related to pembrolizumab.

Note: if after the evaluation the event is determined not to be related, the investigator is instructed to follow the ECI reporting guidance but does not need to follow the treatment guidance. Refer to Section 5.2.1 for dose modification.

It may be necessary to perform conditional procedures such as bronchoscopy, endoscopy, or skin photography as part of evaluation of the event.

- **Pneumonitis:**
  - For **Grade 2 events**, treat with systemic corticosteroids. When symptoms improve to Grade 1 or less, steroid taper should be started and continued over no less than 4 weeks.
  - For **Grade 3-4 events**, immediately treat with intravenous steroids. Administer additional anti-inflammatory measures, as needed.

- Add prophylactic antibiotics for opportunistic infections in the case of prolonged steroid administration.
- **Diarrhea/Colitis:**  
Subjects should be carefully monitored for signs and symptoms of enterocolitis (such as diarrhea, abdominal pain, blood or mucus in stool, with or without fever) and of bowel perforation (such as peritoneal signs and ileus).
  - All subjects who experience diarrhea/colitis should be advised to drink liberal quantities of clear fluids. If sufficient oral fluid intake is not feasible, fluid and electrolytes should be substituted via IV infusion. For Grade 2 or higher diarrhea, consider GI consultation and endoscopy to confirm or rule out colitis.
  - For **Grade 2 diarrhea/colitis** that persists greater than 3 days, administer oral corticosteroids.
  - For **Grade 3 or 4 diarrhea/colitis** that persists > 1 week, treat with intravenous steroids followed by high dose oral steroids.
  - When symptoms improve to Grade 1 or less, steroid taper should be started and continued over no less than 4 weeks.
- **Type 1 diabetes mellitus (if new onset, including diabetic ketoacidosis [DKA]) or ≥ Grade 3 Hyperglycemia, if associated with ketosis (ketonuria) or metabolic acidosis (DKA)**
  - For **T1DM or Grade 3-4 Hyperglycemia**
    - Insulin replacement therapy is recommended for Type I diabetes mellitus and for Grade 3-4 hyperglycemia associated with metabolic acidosis or ketonuria.
    - Evaluate patients with serum glucose and a metabolic panel, urine ketones, glycosylated hemoglobin, and C-peptide.
- **Hypophysitis:**
  - For **Grade 2** events, treat with corticosteroids. When symptoms improve to Grade 1 or less, steroid taper should be started and continued over no less than 4 weeks. Replacement of appropriate hormones may be required as the steroid dose is tapered.
  - For **Grade 3-4** events, treat with an initial dose of IV corticosteroids followed by oral corticosteroids. When symptoms improve to Grade 1 or less, steroid taper should be started and continued over no less than 4 weeks. Replacement of appropriate hormones may be required as the steroid dose is tapered.
- **Hyperthyroidism or Hypothyroidism:**  
Thyroid disorders can occur at any time during treatment. Monitor patients for changes in thyroid function (at the start of treatment, periodically during treatment, and as indicated based on clinical evaluation) and for clinical signs and symptoms of thyroid disorders.

- **Grade 2** hyperthyroidism events (and **Grade 2-4** hypothyroidism):
  - In hyperthyroidism, non-selective beta-blockers (e.g. propranolol) are suggested as initial therapy.
  - In hypothyroidism, thyroid hormone replacement therapy, with levothyroxine or liothyronine, is indicated per standard of care.
- **Grade 3-4** hyperthyroidism
  - Treat with an initial dose of IV corticosteroid followed by oral corticosteroids. When symptoms improve to Grade 1 or less, steroid taper should be started and continued over no less than 4 weeks. Replacement of appropriate hormones may be required as the steroid dose is tapered.
- **Hepatic:**
  - For **Grade 2** events, monitor liver function tests more frequently until returned to baseline values (consider weekly).
    - Treat with IV or oral corticosteroids
  - For **Grade 3-4** events, treat with intravenous corticosteroids for 24 to 48 hours.
  - When symptoms improve to Grade 1 or less, a steroid taper should be started and continued over no less than 4 weeks.
- **Renal Failure or Nephritis:**
  - For **Grade 2** events, treat with corticosteroids.
  - For **Grade 3-4** events, treat with systemic corticosteroids.
  - When symptoms improve to Grade 1 or less, steroid taper should be started and continued over no less than 4 weeks.
- **Management of Infusion Reactions:** Signs and symptoms usually develop during or shortly after drug infusion and generally resolve completely within 24 hours of completion of infusion.

Table 4 below shows treatment guidelines for subjects who experience an infusion reaction associated with administration of pembrolizumab (MK-3475).

Table 4 Infusion Reaction Treatment Guidelines

NCI CTCAE Grade	Treatment	Premedication at subsequent dosing
Grade 1 Mild reaction; infusion interruption not indicated; intervention not indicated	Increase monitoring of vital signs as medically indicated until the subject is deemed medically stable in the opinion of the investigator.	None
Grade 2 Requires infusion interruption but responds	Stop Infusion and monitor symptoms.	Subject may be premedicated 1.5h ( $\pm$ 30 minutes) prior to infusion

NCI CTCAE Grade	Treatment	Premedication at subsequent dosing

promptly to symptomatic treatment (e.g., antihistamines, NSAIDS, narcotics, IV fluids); prophylactic medications indicated for <math>\leq 24</math> hrs
	
Additional appropriate medical therapy may include but is not limited to:
 
 
IV fluids
 
Antihistamines
 
NSAIDS
 
Acetaminophen
 
Narcotics
 
 
Increase monitoring of vital signs as medically indicated until the subject is deemed medically stable in the opinion of the investigator.
 
If symptoms resolve within one hour of stopping drug infusion, the infusion may be restarted at 50% of the original infusion rate (e.g., from 100 mL/hr to 50 mL/hr). Otherwise dosing will be held until symptoms resolve and the subject should be premedicated for the next scheduled dose.
 
Subjects who develop Grade 2 toxicity despite adequate premedication should be permanently discontinued from further trial treatment administration.
	
of pembrolizumab (MK-3475) with:
 
Diphenhydramine 50 mg po (or equivalent dose of antihistamine).
 
Acetaminophen 500-1000 mg po (or equivalent dose of antipyretic).

Grades 3 or 4
 
Grade 3: Prolonged (i.e., not rapidly responsive to symptomatic medication and/or brief interruption of infusion); recurrence of symptoms following initial improvement; hospitalization indicated for other clinical sequelae (e.g.,
	
Stop Infusion.
 
Additional appropriate medical therapy may include but is not limited to:
 
 
IV fluids
 
Antihistamines
 
NSAIDS
 
Acetaminophen
 
Narcotics
 
Oxygen
 
Pressors
 
Corticosteroids
 
Epinephrine
 
	
No subsequent dosing

NCI CTCAE Grade	Treatment	Premedication at subsequent dosing
renal impairment, pulmonary infiltrates)  Grade 4: Life-threatening; pressor or ventilatory support indicated	Increase monitoring of vital signs as medically indicated until the subject is deemed medically stable in the opinion of the investigator. Hospitalization may be indicated. Subject is permanently discontinued from further trial treatment administration.	
Appropriate resuscitation equipment should be available in the room and a physician readily available during the period of drug administration.		

